6.3.1.4 Subgroup analysis

The on-treatment and treatment policy efficacy analyses for the primary endpoint and the secondary endpoints based on bleeding episodes will be repeated for the following subgroups:

- Hemophilia type (Type A vs B)
- Number of bleeding episodes during the 6 months prior to study (≤ 10 vs > 10)
- Age group, years (< 18 , $18-64$, ≥ 65)

In addition, region- and/or country-specific analyses will be performed to support regulatory submission as needed.

Negative binomial regression model will be applied only for subgroups that have at least 3 patients in each treatment arm and the model converges. Otherwise, only summary statistics will be presented.

6.3.2 Secondary endpoints

6.3.2.1 ABR in the treatment period (Global Protocol), ABR in the efficacy period (US Protocol)

Analysis will include all bleeding episode data in the specified period. The on-treatment and treatment policy efficacy analyses will be repeated with this endpoint.

6.3.2.2 Annualized spontaneous bleeding rate in the efficacy period

Analysis will include spontaneous bleeding episodes occurring in the efficacy period. The on-treatment and treatment policy efficacy analyses will be repeated with this endpoint.

6.3.2.3 Annualized joint bleeding rate in the efficacy period

Analysis will include joint bleeding episodes occurring in the efficacy period. The on-treatment and treatment policy efficacy analyses will be repeated with this endpoint.

6.3.2.4 Haem-A-QoL

The Haem-A-QoL will be provided to patients ≥ 17 years of age and includes 46 items contributing to 10 QoL domains (physical health, feelings, view of yourself, sports and leisure,

work and school, dealing with hemophilia, treatment, future, family planning, partnership and sexuality). Scoring for each item is based on a 5-point Likert scale (never, rarely, sometimes, often, and all the time), and higher scores represent greater impairment. The change from baseline in physical health score and total score of Haem-A-QoL at the end of the study will be analyzed using an analysis of covariance (ANCOVA) model with fixed effects of treatment arm, randomization strata of number of bleeding episodes in the 6 months prior to study entry (≤ 10 vs > 10) and randomization strata of hemophilia type (A vs B), baseline Haem-A-QoL physical health score and total score as covariates. Least square means of the physical health score and total score in each treatment arm and the difference of the least square means of the physical health score and total score in the two arms (along with the 95% CI and p-value) will be presented. The normality assumption based on ANCOVA model will be examined and a sensitivity analysis based on the non-parametric Wilcoxon-Mann-Whitney test will be performed. Domain scores, standardized scale scores, and transformed scale scores for Haem-A-QoL and their changes from baseline will be summarized. The above ANCOVA analysis is based on observed data. For patient with missing assessment due to early withdrawal, a sensitivity analysis will also be performed by imputing the domain score and total score as the worst score if the reason of withdrawal is treatment-related in the corresponding treatment arm, and as the average score for other reasons of withdrawal that are not treatment related in the corresponding treatment arm. The same analysis as main will be performed as a sensitivity analysis by excluding values of those who completed Haem-A-QoL at baseline after first dose of fitusiran.

To evaluate the impact of Covid-19, the same ANCOVA model will also be repeated on Covid-19 unaffected set. In addition, a sensitivity analysis using same ANCOVA model will be performed excluding the data impacted by Covid-19 major/critical protocol deviation. A supportive analysis will be repeated on the patients whose responses level to EQ-5D dimensions “anxiety/depression” is no change or improved from baseline.

To evaluate the association between the change in Haem-A-QoL and other clinical measures, the analysis of change from baseline in the Haem-A-QoL physical health score and total score will be stratified by ABR level (0, > 0 to ≤ 5 , > 5) and concomitant pain medication use (Y, N). The ABR level is based on on-treatment strategy during the efficacy period.

The summary of adherence with Haem-A-QoL measurement will also be provided.

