2.2 Randomization methodology

Patients are randomized 2:1 to the fitusiran treatment arm and the on-demand arm. Randomization is stratified by the number of bleeding episodes in the 6 months prior to Screening (≤ 10 vs > 10) and hemophilia type (hemophilia A or B).

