2.6 Statistical modifications made in the statistical analysis plan

This section summarizes major changes in statistical analysis features made in approved SAP versions from statistical considerations in protocol or previous SAP versions, with emphasis on changes after study start (after the first patient was enrolled). These changes are made before database lock.

The statistical analysis plan history table below gives the timing, rationale, and key details for major changes to the statistical analysis features in the statistical analysis plan.

Statistical analysis plan statistical changes

SAP version number	Date approved	Rationale	Description of statistical changes
2	06-Aug-2019		The sensitivity analysis to include all bleeding events was added in Section 6.3.1.2.
2	06-Aug-2019		The summary statistics for number of patients who lost-to-follow-up and who had each intercurrent event is added in Section 6.3
2	06-Aug-2019		A summary of missing data pattern by treatment arm for patient who doesn't have bleeding data after Day 28 is added in Section 6.3.1.1. A sensitivity analysis based on imputed bleeding data in the efficacy period using multiple imputation (MI) method is added in Section 6.3.1.1.
2	06-Aug-2019		A sensitivity analysis based on zero-inflated negative binomial model is added in Section 6.3.1.2.

SAP version number	Date approved	Rationale	Description of statistical changes
2	06-Aug-2019	To be aligned with protocol amendment 02	The secondary endpoint ‘Change in Haem-A-QOL scores in the treatment period’ is changed to ‘Change in Haem-A-QOL physical health score and total score in the treatment period’ in Section 3.2.1 and Section 5.7. The analysis of physical health score is added in Section 6.3.2.4.
2	06-Aug-2019	To clarify how to calculate domain score when item scores are missing for Haem-A-QOL and Haemo-QOL assessments.	The method to calculate domain score when item scores are missing for Haem-A-QOL and Haemo-QOL assessments is added in Section 8.1.
2	06-Aug-2019		For the change in Haem-A-QOL physical health score and total score, the examination of normality assumption based on ANCOVA model and sensitivity analysis based on the non-parametric Wilcoxon-Mann-Whitney test are added in Section 6.3.2.4. In addition, a sensitivity analysis to handle missing assessment is also specified in Section 6.3.2.4.

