5 GENERAL STATISTICAL METHODS

5.1 Sample size justification

Assuming a mean ABR of 18 with standard deviation (SD) = 14 in the on-demand arm (patients randomized to receive on-demand factor concentrates) and a mean ABR of no more than 4 with SD = 6 in the fitusiran treatment arm (patients randomized to receive fitusiran) in either the efficacy period or treatment period, with a sample size of 32 evaluable patients in on-demand arm and approximately 64 evaluable patients in the fitusiran treatment arm, it is projected that the study will have greater than 90% power for testing treatment difference in mean ABRs. This power estimation was based on negative binomial regression model with a 2-sided Type I error rate of 0.05.

The planned sample size is 120 randomized patients assuming a 20% drop-out rate.

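### The rank test that checks the Haem-A-QoL ANCOVA also drops its baseline and strata adjustment, so a disagreement could not be put down to non-normality

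*SAP*

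**What the plan says.** The main analysis in SAP 6.3.2.4 is of change from baseline in two scores, which "will be analyzed using an analysis of covariance (ANCOVA) model with fixed effects of treatment arm, randomization strata of number of bleeding episodes" and hemophilia type, with "baseline Haem-A-QoL physical health score and total score as covariates". These strata are the randomization factors in SAP 2.2: "Randomization is stratified by the number of bleeding episodes in the 6 months prior to Screening", and by hemophilia type.

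The same section says that normality under the ANCOVA will be examined and that "a sensitivity analysis based on the non-parametric Wilcoxon-Mann-Whitney test will be performed". It attaches no strata, covariate or effect estimate to that test, and does not say how a disagreement with the ANCOVA would be read.

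The change table in SAP 2.6 shows what the test is applied to. It introduces the normality check and the rank test together: "For the change in Haem-A-QOL physical health score and total score, the examination of normality assumption based on ANCOVA model". The variable is therefore the change score.

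In SAP 5.7, Haem-A-QoL is the fifth and last step of the hierarchy, physical health score first and then total score. The rank test is not mentioned there.

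**The concern.** A check on one assumption is easiest to read when it changes only that assumption. Here two things change at once. The ANCOVA assumes normal errors and adjusts for baseline and strata; the rank test drops the normality assumption and the adjustment together. If the two disagree, the reader cannot tell whether non-normality or lost adjustment is responsible.

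The SAP does hold the model fixed in other sensitivity analyses. The Covid-19 analyses of Haem-A-QoL reuse the same ANCOVA, and the treatment-policy and Covid-19 analyses of bleeding reuse the same negative binomial model.

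What is at stake is interpretation. A non-significant rank test beside a significant ANCOVA could cast doubt on a sound quality-of-life result for a reason unrelated to the shape of the data. The SAP gives no SD, effect size or power for this endpoint, so there is no stated margin to absorb such a discrepancy.

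**Working it through.** **The plan's own figure.** SAP 5.1 powers bleeding rate only, "with a sample size of 32 evaluable patients in on-demand arm and approximately 64 evaluable patients in the fitusiran treatment arm", with means 18 (SD 14) and 4 (SD 6). With var(ABR) = μ/t + kμ² and t = 1 year, k = (196 − 18)/324 = 0.55 on demand and (36 − 4)/16 = 2.0 on fitusiran. Using the larger k in both arms, the variance of the log rate ratio is (1/18 + 2)/32 + (1/4 + 2)/64 = 0.0994. Then ln(18/4)/√0.0994 = 4.77, and power is Φ(4.77 − 1.96) = 99.8%. This agrees with the stated figure of above 90%, and 96/(1 − 0.20) = 120 also reproduces. Neither says anything about Haem-A-QoL power.

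**Number likely to be evaluable.** 120 randomized less about 10 adolescents (protocol 4.3) leaves 110. With the assumed 20% drop-out, 110 × 0.8 = 88, and 2:1 allocation gives about 29 vs 58. This is approximate: the protocol counts adolescents as under 18, while the questionnaire is given from age 17.

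**Change score against ANCOVA.** For baseline-to-end correlation r and unit score variance, a change score has variance 2(1 − r) and the ANCOVA residual has 1 − r². The ratio is 2/(1 + r), or 1.43, 1.25 and 1.11 at r = 0.4, 0.6 and 0.8. Under normality, the asymptotic efficiency of the rank test on change relative to ANCOVA is 0.955(1 + r)/2, or 0.62, 0.72, 0.81 and 0.91 at r = 0.3, 0.5, 0.7 and 0.9.

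**Simulation 1: planned test against rank ANCOVA on baseline.** 29 vs 58 patients, difference 0.5 SD, two-sided 5%, r = 0.4/0.6/0.8.

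| Errors | Planned test | Rank ANCOVA | Gain (points) |
|---|---|---|---|
| Normal | 49/63/93% | 61/72/95% | 12/9/2 |
| Heavy-tailed (t, 3 df) | 63/83/99% | 82/92/99% | 19/9/0 |
| Skewed (lognormal) | 73/93/100% | 95/99/100% | 22/6/0 |

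**Simulation 2: planned test against the ANCOVA it checks.** 32 vs 64 patients, effect set for about 80% ANCOVA power, 3,000 trials per setting, r = 0.3/0.5/0.7/0.9. Hemophilia B share is 26/120. A 50:50 prior-bleed split and a prior-bleed effect of 0.3 residual SD are assumed.

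| Errors | ANCOVA | Planned test | Rank ANCOVA, stratified |
|---|---|---|---|
| Normal | 0.79/0.78/0.79/0.79 | 0.58/0.65/0.70/0.75 | 0.72/0.73/0.74/0.75 |
| Heavy-tailed | 0.82/0.82/0.82/0.82 | 0.70/0.79/0.87/0.92 | 0.92/0.93/0.94/0.94 |
| Skewed | 0.80/0.79/0.79/0.79 | 0.76/0.83/0.93/0.98 | 0.99/0.99/0.99/0.99 |

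Null rejection, run at r = 0.5 for each error shape, was 0.040 to 0.056 across the methods.

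The heavy-tailed row at r = 0.3 shows the problem. Ranks with the adjustment kept gain 10 points on the ANCOVA (0.92 vs 0.82). The planned test loses 12 (0.70 vs 0.82), so it moves the wrong way in a situation it is there to detect.

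**The case against.** The strongest reply is that this is a choice between valid sensitivity tests. The test holds its size and gates nothing, and no text says that it replaces the ANCOVA if normality fails. Normality is also examined directly in the same sentence, so the rank test need only show whether the conclusion survives without the assumption. Agreement would be informative, and the residual check helps with disagreement. All of this stands, and it is why the point is minor. It does not remove the ambiguity when the two analyses disagree, which is when the check is needed.

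Three stronger readings are tempting, and the material does not support them.

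- A reader might infer that the test ignores baseline. SAP 2.6 ties it to the change scores, so baseline is subtracted; it is only not used as a covariate.
- A reader might infer that the test is weaker than the ANCOVA in general. It is 4 to 21 points weaker under normal errors. Under heavy-tailed or skewed errors it is weaker at r = 0.3, mixed at 0.5 and stronger at 0.7 and above. The documents give no error shape or correlation to settle which applies.
- A reader might infer that the trial's one claim independent of bleeding is at risk. The confirmatory p-value comes from the ANCOVA. SAP 6.3.2.4 itself plans to stratify the score change by ABR level to study their association, so independence from bleeding is not something the plan asserts.

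Nor does leaving out the strata cost power by itself. In the second simulation under normal errors, a van Elteren test on change gave 0.57/0.64/0.68/0.73 against 0.58/0.65/0.70/0.75 for the plain test. The gain comes from the baseline covariate.

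**Conclusion.** The point holds in a limited form. The planned rank test differs from the ANCOVA in adjustment as well as in distributional assumption, so disagreement between them could not be assigned to non-normality. A rank ANCOVA removes most of that ambiguity. Its simulated power was at or above that of the planned test in every setting, by up to 22 points at r = 0.4 and by 2 points or less at r = 0.8 in the first simulation.

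The sizes rest on assumptions that the documents do not supply: the correlation, the 0.5 SD difference and the error shapes. The evaluable number is derived from the planned enrolment and drop-out. The simulated figures are approximate. The attribution argument needs none of these assumptions, because it follows from the two specifications side by side.

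The confirmatory conclusion is not affected. This is a free improvement of low priority.

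**What to change.** In SAP 6.3.2.4, replace the Wilcoxon-Mann-Whitney test with a rank ANCOVA for each score: rank the change, adjust for the ranked baseline value of that score, and compare arms with stratification by the two randomization factors. Add a sentence that the ANCOVA remains the confirmatory analysis for step 5 of the hierarchy whatever the rank analysis shows. A stratified rank test without the baseline covariate would not be an adequate substitute.

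The cost is one or two sentences in the SAP. No new data are needed, since baseline scores and strata are already in the main model, and standard software suffices.

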^r Blood samples for PK analysis will be collected at the timepoints listed in Table 7 in all fitusiran arm patients. In East Asian patients in the fitusiran arm at East Asian sites, blood samples for PK analysis will be collected at the time points listed in Table 8 (which includes those time points listed in Table 7), and pooled urine for PK analysis will be collected at the time points listed in Table 9.

^s Must be completed at the clinic. Will be collected at EOS visit, not be collected at ET visit.

^t Will include review of entries, (symptoms of bleed events, bleed causality, bleed severity, doses administered), whether appropriate site contact occurred regarding treatment of bleeds, and review of patient bleed management plan and recommendations and requirements for site contact regarding dosing.

^u It is preferred that factor concentrate administration and bleeding events are entered in the eDiary immediately or within 24 hours. Additional patient follow-up may be required as described in Section 7.2.1. Patients in the fitusiran treatment arm who present in the clinic with symptoms characteristic of a potential bleeding episode should have assessments completed per Table 2.

^v Perioperative assessment of safety and hemostatic efficacy only in patients undergoing operative procedures while on study (see Table 10).

^w AEs will be monitored and recorded from date of signed informed consent through Follow-Up. Signs and symptoms of thrombosis will be evaluated at every visit (see Section 6.5).

^x In addition to recording concomitant medications, documented history of prior medications will be collected during Screening.

Table 2: Bleeding Episode Assessments – Unscheduled Visit

| | Predose | Postdose 10 min (± 5 min) ^d | Postdose 60 min (± 5 min) ^d |
|--|---------|--|--|
| Directed Physical Examination ^a | X | | |
| Vital Signs | X | | |
| AT | X | | |
| FVIII/IX Levels | X | X | X |
| TG | X | X | X |
| Coagulation | X | X | X |
| Hematology | X | X | X |
| Exploratory Coagulation ^b | X | | X |
| Optional Imaging ^c | X | | |

Abbreviations: AT=antithrombin; BPAs=bypassing agents; FVIII=factor VIII; FIX=factor IX; TG=thrombin generation

^a See Section 7.5.3 for assessments to be performed during a directed physical examination.

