5.3.1. Discontinuation of Investigational Medicinal Product

The Investigator or designee may discontinue dosing in a patient if the patient:

- Is in significant violation of the protocol
- Is non-adherent to treatment regimen
- Experiences a serious or intolerable AE, a life-threatening bleeding episode, eg, any gastrointestinal hemorrhage or intracranial hemorrhage, or life-threatening thromboembolic event
- Requires a prohibited medication.

The Investigator will confer with the Sponsor or study Medical Monitor before discontinuing dosing in the patient.

Patients (or their guardians) may decide to discontinue IMP.

In general, patients who discontinue IMP dosing for any reason will be encouraged to remain on the study to complete the remaining assessments through the end of study so that their experience is captured in the final analyses. If a patient discontinues dosing due to a serious adverse event (SAE), the SAE should be followed as described in Section 7.5.6. When a patient discontinues IMP dosing, the primary reason must be recorded in the appropriate section of the eCRF. Patients who discontinue IMP but who remain on study may receive treatment consistent with local standard practice for their disease per Investigator judgment, as applicable. Safety will be captured for the entire duration of study for patients who discontinue treatment.

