5.7 Multiple comparisons/multiplicity

To control for the familywise error rate at 0.05 level in the testing of primary and selected secondary endpoints, a hierarchical testing approach will be used. The endpoints will be tested in the following order:

Global protocol	US protocol	2-Sided alpha
1. ABR in the efficacy period	1. ABR in the treatment period	0.05
2. ABR in the treatment period	2. ABR in the efficacy period	0.05
3. Annualized spontaneous bleeding rate in the efficacy period		0.05
4. Annualized joint bleeding rate in the efficacy period		0.05
5. Change in Haem-A-QOL physical health score and total score in the treatment period		0.05

If testing of any of the endpoints is not statistically significant, formal testing of subsequent endpoints will stop and the null hypothesis for subsequent tests will not be rejected. For endpoint 5, change in Haem-A-QOL physical health score in the treatment period will be tested first followed by change in Haem-A-QOL total score in the treatment period. The testing of the secondary endpoint ABR in the onset period will not be included in this hierarchical testing procedure.

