6 STATISTICAL ANALYSES

6.1 Patient disposition

Patient disposition will be tabulated for the following categories:

- patients screened
- patients screen failed
- patients randomized
- patients in each analysis population
- patients treated (fitusiran arm only)
- patients who completed the study treatment (9-month treatment period, fitusiran arm only)
- patients who discontinued study drug and primary reasons for study drug discontinuation (fitusiran arm only)
- patients who discontinued study drug and primary reasons for study drug discontinuation due to Covid-19 (fitusiran arm only)
- patients who completed the study
- patients who withdrew prior to completing the study but completed Month 9 visit
- patients who withdrew prior to completing the study and primary reasons for withdrawal.
- Patients who withdrew prior to completing the study and primary reasons for withdrawal due to Covid-19

Patient disposition will be presented by randomized treatment arm and overall, as applicable.

Patients randomized by country, site and randomization stratification factor stratum will be summarized by randomized treatment arm and overall.

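### The only imputation-based check of Haem-A-QoL dropout analyses one fixed value per patient as if observed; where that value is the arm average, the estimate stays put and its standard error is understated

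*SAP*

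**What the plan says.** SAP 6.3.2.4 fits an ANCOVA to the change in the physical health and total scores at end of study, with treatment arm, the two randomization strata and baseline scores in the model. On missing data it says "The above ANCOVA analysis is based on observed data".

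For scores missing through early withdrawal it adds one sensitivity analysis with two branches. The first is "imputing the domain score and total score as the worst score if the reason of withdrawal is treatment-related in the corresponding treatment arm". The second is "as the average score for other reasons of withdrawal that are not treatment related in the corresponding treatment arm". No repeated draws and no variance correction are specified.

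The remaining Haem-A-QoL checks are the Wilcoxon-Mann-Whitney test, exclusion of baselines completed after the first dose, the Covid-19 analyses, the EQ-5D anxiety/depression subset, and stratification by bleeding rate and pain medication. None of them fills in a withdrawn patient. Otherwise missingness is only described: "The summary of adherence with Haem-A-QoL measurement will also be provided", and SAP 6.1 tabulates "patients who withdrew prior to completing the study and primary reasons for withdrawal".

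Three other places set the context:
- Protocol Table 1, footnote s, on the questionnaires: "Will be collected at EOS visit, not be collected at ET visit". A patient who leaves the study early therefore has no score after baseline.
- Protocol 5.3.1: patients who stop the drug "will be encouraged to remain on the study to complete the remaining assessments through the end of study". Those who stay can still give an end-of-study score.
- SAP 5.7: these scores are the last step of the testing hierarchy, and "change in Haem-A-QOL physical health score in the treatment period will be tested first", followed by the total score.

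For bleeding counts, SAP 6.3.1.2 specifies multiple imputation under missing at random (MAR) and copy-reference, combined by Rubin's formula.

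**The concern.** A sensitivity analysis for dropout should ask whether the result survives a plausible alternative for the missing scores, and its interval should reflect that those scores are unknown. Filling in the observed arm mean does neither. It restates the completers' arm difference and adds pseudo-observations that the model counts in full. A reader who sees the main estimate repeated with a narrower interval may take that as corroboration.

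At stake is how far the two Haem-A-QoL results, self-reported in an open-label trial, can be called robust to withdrawal. The formal test is not at stake.

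**Working it through.** **1. The plan's own figure.** SAP 5.1 needs 64 + 32 = 96 evaluable patients and assumes 20% dropout: 96 / (1 - 0.20) = 120, as stated. That is planning for the bleeding rate. The documents give no sample size, SD, effect or missing rate for Haem-A-QoL.

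**2. Closed form, no covariates.** Let a fraction d of each arm be missing and filled with the arm mean.
- The estimate is the completers' difference, so its true SE is proportional to σ/√((1-d)n).
- The residual sum of squares comes from completers only but is divided by roughly the full n. The model's variance is therefore about (1-d)σ², and the reported SE is proportional to σ√(1-d)/√n.
- Reported/true SE = 1 - d, whatever σ is. Coverage = 2Φ(1.96(1-d)) - 1.

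| d | SE ratio | Coverage | Error of a nominal 5% test |
|---|---|---|---|
| 5% | 0.95 | 93.7% | 6.3% |
| 10% | 0.90 | 92.2% | 7.8% |
| 20% | 0.80 | 88.3% | 11.7% |

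**3. Simulation of the planned ANCOVA, all withdrawals average-filled.** The following are assumed and are not in the documents:
- 75 and 37 patients aged 17 or over (112 of the 120)
- score mean 40, SD 17, true effect -8
- baseline to end-of-study correlation (r) 0.4, 0.6 or 0.8
- missing completely at random
- *average* read as the arm's mean observed end-of-study score

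Whole-patient rounding gives 5.4%, 10.7% and 19.6% missing. There were 5,000 runs per case.

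| Missing | Reported/true SE (r = 0.4 / 0.6 / 0.8) | Coverage |
|---|---|---|
| 20% | 2.89/3.62 = 0.80; 2.61/3.23 = 0.81; 2.16/2.74 = 0.79 | 88.3 / 89.1 / 88.1% |
| 10% | 0.90 / 0.89 / 0.88 | 92.3 / 92.1 / 91.1% |
| 5% | 0.94 / 0.93 / 0.95 | 93.6 / 93.2 / 94.1% |

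The observed-data ANCOVA covers 94-95% throughout. In a separate run at r = 0.6 and 20% missing, the estimate was -7.88 after filling and -7.90 on observed data.

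**4. Why the SE is wrong in a baseline-adjusted model.** A fixed end score ignores the patient's baseline and strata, so filled patients do have residuals. At 20% missing the residual SD, filled versus observed, is 5.4 v 15.2, 7.8 v 13.4 and 10.3 v 10.3 at r = 0.4, 0.6 and 0.8. At low correlation the understatement comes mainly from the small filled residuals. At 0.8 the reported SE is only about 7% below that of the main ANCOVA (2.16 v 2.32). The rest arises because the fill makes the estimator noisier (true SE about 2.78 v 2.37). In every case each filled score counts as a full observation.

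**5. Mixed reasons for withdrawal** (20% missing, r = 0.6, 3,000 runs; 25% and 50% of withdrawals given the worst score).

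| *Worst* means | Applied in | Reported/true SE (25% / 50%) |
|---|---|---|
| Worst observed in arm | both arms | 0.96 / 1.03 |
| Worst observed in arm | fitusiran only | 0.91 / 0.97 |
| Scale maximum, assumed 100 | both arms | 1.29 / 1.64 |
| Scale maximum, assumed 100 | fitusiran only | 1.13 / 1.40 |

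With the worst observed score, the estimate moves 0.2-0.5 points if both arms are affected, and 2.1-4.2 points against fitusiran if only that arm is.

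**6. The alternative** (20% missing completely at random, r = 0.6, 1,500 runs, 25 imputations). Observed-data ANCOVA: -7.90, SE 3.09. Multiple imputation under MAR: -7.90, SE 3.12, coverage 94.2%. Copy-reference: -6.32, SE 3.11, a shift of 7.90 - 6.32 = 1.58 points.

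**The case against.** The strongest reply is that the planned check is not mean imputation alone. Its first branch gives the worst score to treatment-related withdrawals, and step 5 shows this can move the estimate further against fitusiran than copy-reference does. That stands. A reader might infer that the check as a whole cannot move the estimate or reveal a loss of effect; the SAP sentence does not support that. The SE understatement describes the whole check only when few withdrawals are classed as treatment-related.

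A reader might also score the average fill against a truth in which fitusiran patients lose all benefit after withdrawal, and report still lower coverage. That builds in an estimand the SAP does not state for Haem-A-QoL. For bleeding it prefers the on-treatment estimand, and on a similar reading the average fill is not biased in that scenario. Only the variance argument is used here.

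Other objections stand in part:
- The size rests on assumed inputs, and at 5% missing it is small. Patients who stop the drug are encouraged to stay, so Haem-A-QoL missingness may be well below 20%.
- MAR imputation will largely reproduce the main ANCOVA.
- Copy-reference with Rubin's rules overstates the SE by about 25% at 20% missing.
- The bleeding imputation cannot be reused as it is, because it models recurrent counts and conditions on counts before withdrawal.

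None of this justifies analysing a filled mean as an observation, or leaving *worst* undefined.

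**Conclusion.** The point holds in a limited form and is minor. The check carries no imputation uncertainty in either branch. For withdrawals classed as not treatment-related it returns the observed-data estimate with too small an SE: about 0.8 of the true value at 20% missing, 0.9 at 10% and 0.95 at 5%, if all withdrawals fall in that class and are missing completely at random. The closed form gives the same ratios without an assumed SD; the simulated coverage depends on the assumed inputs above. With a mix of reasons, the direction of the SE error depends on the mix and on what *worst* means. The phrase about the corresponding arm favours the worst observed score in that arm, but the text does not say so.

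A reader might infer that the confirmatory Haem-A-QoL result or the familywise error rate is compromised. The documents do not support this: the formal test is the observed-data ANCOVA, and no success criterion uses the check. Nor is footnote s of Protocol Table 1 a contradiction; it only explains why early withdrawals have no later score.

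**What to change.** In SAP 6.3.2.4, replace the arm-average fill with wording such as:

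> Missing end-of-study scores will be multiply imputed (100 imputations) from a continuous-outcome model with treatment arm, randomization strata and the patient's own baseline score. The benchmark assumes MAR. The stress test uses copy-reference: fitusiran withdrawals are imputed from the on-demand arm, and on-demand withdrawals from their own arm. Each completed data set is analysed with the main ANCOVA and combined by Rubin's rules.

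If the worst-score scenario is kept, report it separately as a stress test. State whether *worst* is the worst observed score in the arm or the scale maximum, and which recorded withdrawal reasons count as treatment-related.

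The cost is SAP wording and a little more analysis work before database lock; no new data and no protocol amendment are needed. The report should say that the MAR run is expected to match the main ANCOVA and that the copy-reference SE is conservative.
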